## 1. STUDY OVERVIEW

---

**Background and rationale** Knee arthroplasty is a common procedure performed worldwide to improve the quality of life for patients with degenerative knee conditions, trauma, and tumours. Complications can occur after knee arthroplasty, which may lead to a revision procedure, where at least one implant is exchanged, added, or removed. As the number of primary procedures in the world is increasing, so is the corresponding number of revisions. Some patients may require additional revision procedures, and some may end in a negative spiral of repeated revisions; We define three or more revisions on the same knee as being 'multiply revised'. The clinical impression of multiply revised patients is that the repeated occurrence of complications has significant impacts on the patients' quality of life including chronic pain, decreased independence, and increased morbidity. No study has yet investigated the incidence and prevalence of multiply revised knee arthroplasty patients stratified by previous revisions. To improve the care of multiply revised patients, epidemiological information is required which is the rationale of this study.

**Objectives** The aim of this observational study is to investigate the incidence and prevalence of multiply revised knee arthroplasty patients in all Danish patients with primary knee arthroplasty.

**Hypothesis** The number and burden of knee arthroplasty revision procedures and patients in Denmark has increased dramatically in the last 23 years.

**Methods** This is an observational study. Data will be collected from all primary and revision knee arthroplasties performed in Denmark from January 1st 1998 to 31st December 2021. Data will be acquired from two registers: The Danish Knee Arthroplasty Register (DKR), containing surgeon-reported data on primary and revision knee arthroplasties. In addition, data will be acquired from Landspatientregisteret, which contains all clinical data collected during any visit to a public or private healthcare facility in Denmark.

### PICOTS

**Population:** All Danish citizens who have received a primary knee arthroplasty at a Danish healthcare facility, from the 1st of January 1998 to the 31st of December 2021

**Intervention/Exposure** Multiple revision knee arthroplasties in the same knee

**Comparator:** None

**Outcome (primary):** Annual standardized prevalence and incidence of n-grade revisions following knee arthroplasty between 1998 and 2021 in Denmark.

**Time:** Retrospectively, from the 1st of January 1998 to the 31st of December 2021, i.e., up to 24 years follow-up.

**Study design:** Observational retrospective register study.

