Since 1998, the Danish Knee Arthroplasty Register has registered knee replacements (both primary and revisions) performed in Denmark. Traditionally, the most important measure within register research of knee replacements has been the cumulative revision rate, which describes how many patients experience a revision after a given period of time. Around 13% of primary knee arthroplasties are revised for the first time within the first 20 years in Denmark. In the last 20 years, more than 20,000 revisions have been performed. In 2020, 1048 were performed (3).

As the number of performed annual primary procedures increases, so will the number of annual revisions. Upfill-Brown et al. examined the number of revisions in the United States in the period 2012 to 2019. The number of revisions increased by 29.6% per year (4). See **Figure 1**. Kurtz et al. and Pavel et al. have projected, on the basis of large national registries in the USA and England, containing several hundreds of thousands of patients, that the annual number of revisions after primary knee arthroplasty will increase over 300% in England and over 600% in the USA in 2030 compared to the number of revisions in 2005 (2, 5). See **Figure 2**.

Figure 1: Projection of the annual incidence of performed revisions in the United States.

From Uffill-Brown et al.

[figure not shown]
[figure not shown]

Fig. 2

The projected number of revision total hip arthroplasty (THA) and total knee arthroplasty (TKA) procedures in the United States from 2005 to 2030.

Figure 2: Projection of the annual incidence of revisions carried out in England and Wales.

From Patel et al.

Graph showing the projected total number of revision knee arthroplasties in England and Wales between 2013 and 2030.

[figure not shown]
Re-revision

Unfortunately, even after revision, there is a risk of new complications, which may necessitate another revision (re-revision). In some patients, one complication follows another, and these patients may require several revisions. We use the term *multiply revised* when a patient experience at least three revisions of their knee replacement. In principle, there is no upper limit to the number of revisions in a knee, and some knees are revised more than 10 times. Some patients may end with an arthrodesis or amputation (6, 7).

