Landspatientregisteret (LPR) is a national and clinical database administered by the Danish Health Authority since 1976. All information generated when a patient is treated by the public health service is reported here. In addition to information regarding procedures and admissions, the register contains information on residence, partner status, level of education, income, comorbidities and emigration amongst others. Operations are recorded according to the NOMESCO classification, while diagnoses are coded according to the ICD-10 classification.

Identification of primary procedures

We will determine the cohort of primary procedures from DKR (called P-DKR) by identifying all primary procedures performed from January 1st 1998 to December 31st 2021. P-DKR is then transferred to Danmarks Statistik (DS). Through DS, all primary procedures in the observation period will be identified using NOMESCO operation codes (KNGB*) and these will be collected in a cohort called P-SD. P-DKR and P-SD will be joined into a cohort called PRIM and this cohort will best describe all primary procedures performed in Denmark during the observation period.

Identification of revision procedures

The DKR cohort of revisions (R-DKR) will be identified by all registrations marked as revisions during the observation period. R-DKR is also transferred to DS. All revisions will be identified in DS as R-DS using the NOMESCO operation codes KNG* (knee procedure), KNGC* (revision of knee), KNGG* (arthrodesis) and KNFQ19 (femur amputation). The cohorts R-DKR and R-DS will be combined and called REV. This cohort will best describe revision procedures performed in Denmark during the observation period.

Insertion of cement spacers presents a special registration problem, as different registration practices exist. Some use KNGS codes (eg KNGC59A – Insertion of spacer in a knee joint in connection with revision). We intend to not consider spacer insertion as a revision. For example a two-stage revision will be considered as one revision.

Organization of data

A table (G) with PRIM and REV will be created. G will contain information on revisions, deaths, disappearances, emigration and the associated dates. For each knee joint in PRIM and for each date in the observation period, it will be possible to describe the status of the knee joint.

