Calculation of standardized incidence: Annual standardized incidence is calculated as the number of new n-grade revisions performed as a proportion of the population in Denmark during a specific year. The population size of Denmark is defined as the population size at January 1st for that year (3). The incidence is then multiplied by 100,000 for standardization. This is done for each level of revision, each year. E.g., the standardized incidence for 1998 is calculated as:

$$\text{Standardized incidence, 1998} = \frac{\text{Number of new } n - \text{ grade revisions in the population in 1998}}{\text{Total population in Denmark in 1998}} * 100,000$$

Missing data: We expect to encounter some missing data. All missing data will be described.

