Timing of outcome assessments	14	Time points at which the outcomes are measured including visit "windows"	2. Tabular presentation of timing of outcome measurements
Section 4: Statistical Principles			
	15	Level of statistical significance	1. Study overview

Confidence intervals and P values	16	Description and rationale for any adjustment for multiplicity and, if so, detailing how the type 1 error is to be controlled	1. Study overview
	17	Confidence intervals to be reported	1. Study overview
Adherence and protocol deviations	18a	Definition of protocol deviations for the study	4. Protocol deviations with bearing on this statistical analysis plan
	18b	Description of which protocol deviations will be summarized	4. Protocol deviations with bearing on this statistical analysis plan
Analysis populations	19	Definition of analysis populations, eg, intention to treat, per protocol, complete case, safety	5. Outline (for each table and figure)
Section 5: Study Population			
Screening data	20	Reporting of screening data (if collected) to describe representativeness of trial sample	5. Outline (Figure 1)
Eligibility	21	Summary of eligibility criteria	1. Study overview
Recruitment	22	Information to be included in the STROBE flow diagram	5. Outline (Figure 1)
Withdrawal/follow-up	23a	Level of withdrawal, e.g., dropouts after inclusion or refusal to be contacted for additional information	5. Outline (Figure 1)
	23b	Timing of withdrawal/lost to follow-up data	5. Outline (Figure 1)
	23c	Reasons and details of how withdrawal/lost to follow-up data will be presented	5. Outline (Figure 1)
Baseline patient characteristics	24a	List of baseline characteristics to be summarized	5. Outline (Table 1)
	24b	Details of how baseline characteristics will be descriptively summarized	5. Outline (Table 1)
Potential confounding covariates	25	A description of potential confounding covariates and how these will be dealt with	-
Section 6: Analysis			
Outcome definitions	List and describe each primary and secondary outcome including details of:		
	26a	Specification of outcomes and timings. If applicable include the order of importance of primary or key secondary endpoints (e.g., order in which they will be tested)	5. Outline (mainly Table 2)
	26b	Specific measurement and units (e.g., glucose control, HbA1c [mmol/mol or %])	5. Outline

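### The SAP's population of patients with a primary from 1998 conflicts with its national revision rates: taken as written it drops older knees and builds in a rise, and read the other way it leaves revisions without a grading rule

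*SAP*

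**What the plan says.** Some passages tie the study to primaries from 1998:

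- SAP section 1, PICOTS, gives the population as "All Danish citizens who have received a primary knee arthroplasty at a Danish healthcare facility", with dates from 1 January 1998 to 31 December 2021. Item 21 of SAP Table A ("Summary of eligibility criteria") refers the reader to section 1, where this line is the only eligibility statement.
- The protocol (Identification of primary procedures) forms its primary cohort, PRIM, by "identifying all primary procedures performed from January 1st 1998 to December 31st 2021". Under Organization of data, the status of a knee can be described "For each knee joint in PRIM and for each date in the observation period".

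Others describe a national count of revisions:

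- SAP section 1, Methods: "Data will be collected from all primary and revision knee arthroplasties performed in Denmark from January 1st 1998 to 31st December 2021".
- The protocol's DKR revision cohort, which feeds the combined cohort REV, is "identified by all registrations marked as revisions during the observation period". No condition is set on the date of the primary.
- SAP section 3 calculates incidence as "the number of new n-grade revisions performed as a proportion of the population in Denmark during a specific year", with all living citizens on 1 January as denominator. The protocol's WPA1 formula has the same national form.

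The only limit stated in SAP section 3 restricts prevalence by the date of the revision. It does not mention incidence or the date of the primary. SAP section 4 lists no deviation from the protocol.

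**The concern.** Take a revision in 2002 of a knee replaced in 1994. It falls inside the window and belongs in REV, but the patient is outside the stated population unless he or she also had a primary from 1998 on. A cohort defined by its primaries suits the cumulative revision rates of WP-A2. It does not match a denominator of all Danes.

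The loss is uneven over time. In 1998 only knees replaced that same year could contribute a first revision, and the pool then fills year by year. This affects even grade 1, and it favours the SAP's hypothesis of a dramatic increase over 23 years. It also differs from missing knowledge of revisions before 1998, because the operations concerned are in the data already held.

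**Working it through.** The documents give no expected incidence, so there is no planned figure to reproduce. The check asks how much a 1998 start for primaries could distort grade 1 incidence.

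**Inputs from the protocol.** About 13% of primaries have a first revision within 20 years, and 1,048 revisions of all grades were done in 2020 (Size of the problem). There were more than 150,000 primaries in 20 years and about 10,500 in 2020 (Background).

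**Assumptions, varied.**

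- Time to first revision is Weibull, F(t) = 1 − exp[−(t/s)^k], with s = 20/(−ln 0.87)^(1/k), so that F(20) = 0.13. Shape k is 1.0, 0.7 or 0.5, giving a first-year risk of 0.7%, 1.7% or 3.1%.
- Mortality is 0 or 4% a year.
- Primary volume is flat at 150,000/20 = 7,500 a year, or a linear ramp with 150,000 primaries over 2001-2020 and 10,500 in 2020. The ramp's slope is (10,500 − 7,500)/9.5 = 315.8 a year, which gives 10,500 − 22 × 315.8 ≈ 3,553 in 1998.

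First revisions in a year are the sum, over monthly cohorts of primaries, of N × [F at the end of the year − F at its start], weighted by survival. This was run with primaries from 1998 only and again with primaries back to 1978.

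**One case by hand** (flat volume, k = 1, no deaths; hazard 0.1393/20 = 0.00696 a year):

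- 1998, restricted: 7,500 × 0.00696/2 ≈ 26. Unrestricted: 7,500 × F(20.5) = 7,500 × 0.133 ≈ 998. Share captured: 26/998 ≈ 3%.
- 2021, restricted: 7,500 × F(23.5) = 7,500 × 0.151 ≈ 1,132. Unrestricted: 7,500 × F(43.5) = 7,500 × 0.261 ≈ 1,960.
- Rise 1998 to 2021: 43.5-fold restricted, 2.0-fold unrestricted.

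**All cases** (ranges over the three shapes):

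| Volume, mortality | Captured 1998 | Captured 2020 | Unrestricted rise 1998-2021 | Restricted rise 1998-2021 | Unrestricted first revisions 2020 |
|---|---|---|---|---|---|
| Flat, 0 | 3-16% | 57-75% | 1.4-2.0 | 6.8-43.5 | 1,378-1,921 |
| Flat, 4% | 4-20% | 75-89% | 1.2-1.4 | 5.3-28.9 | 898-962 |
| Ramp, 0 | 9-31% | 91-96% | 5.1-8.8 | 16.1-88.1 | 1,127-1,176 |
| Ramp, 4% | 10-33% | 95-98% | 4.4-6.8 | 13.2-63.2 | 770-945 |

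Across all cases the share captured is 23-83% in 2003 and 37-92% in 2008. The restricted count in 1998 is 12-73 (ramp) or 26-154 (flat).

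**Plausibility.** The runs without deaths give more first revisions in 2020 than the 1,048 revisions of all grades that the protocol reports, so their extremes are the less credible. The runs with 4% mortality alone still give 4-33% captured in 1998 and 75-98% in 2020. The ramp falls to zero 10,500/315.8 ≈ 33 years before 2020, about 1987, so it leaves few old knees and probably understates the loss. Flat volume ignores the growth described in the protocol's Background and probably overstates it. Higher grades and prevalence were not modelled.

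**The case against.** The strongest reply is that the exclusion is inferred. No sentence says that revisions of older knees are dropped. The protocol's Design section speaks of including everyone operated on in 1998-2021, and REV and both incidence formulas set no condition on the primary. The limit on prevalence by revision date would be empty if only knees with a primary from 1998 counted, since such knees cannot have an earlier revision. The flow diagram, which might settle the matter, is not visible. This stands, so a reader who infers that the plan certainly discards every such revision goes too far. PICOTS also defines people rather than knees, so an older knee in a patient with another primary from 1998 on could enter.

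This reading does not rescue the plan. If every revision counts, nothing says how to grade one without a linked primary, and the first one observed may be labelled grade 1 when it is not.

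Two further inferences are tempting but unsupported:

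- That incidence would start near zero and rise about 16-fold with no real change. This follows from constant volume and an exponential time to first revision with mean 8 years (shares of 0.060 in 1998 and 0.947 in 2021, ratio 15.8). The 8 years come from a cited single-centre study of 300 patients, and the protocol says that volume grew. It is one scenario.
- That the register's totals prove the true series flat. More than 20,000 in 20 years is a lower-bound average of 1,000 a year; set against 1,048 in 2020, it says nothing about 1998-2000.

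It can also be said that a cohort followed from its primary has known grades, that the SAP's objective refers to patients with a primary, and that no test is planned. The first two are good reasons to keep that cohort as a second series. The third does not help, because the annual curves are themselves the evidence for the hypothesis. Starting the trend later would reduce the artefact but restore none of the omitted operations.

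**Conclusion.** The concern holds as a conflict between the stated population and the national outcome, with a defect under either reading. Taken as written, grade 1 incidence is too low throughout, most in the early years, and carries a built-in rise: about 3-33% captured in 1998 and 57-98% in 2020. With flat volume, a true 1.2-2.0-fold rise could appear as 5-44-fold; with ramped volume, a true 4.4-8.8-fold rise as 13-88-fold. In every case examined the restriction inflates the rise. The size rests on assumed volumes, hazard shapes and mortality, and should not be quoted as an estimate of the study's bias. Under the other reading the numerator is national, but the grades of knees without a linked primary are undefined. The matter should be settled before the SAP is accepted, because the final analysis follows that step.

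**What to change.** 1. Reconcile the PICOTS population, the protocol's PRIM-based status table and the incidence definition in SAP section 3. Record any change in SAP section 4.
2. For national incidence and prevalence (Tables 2-3, Figures 2-3 and the supplement), count every eligible revision in REV performed in 1998-2021, whatever the date of the primary.
3. Add the DKR field *Number of previous revisions* to the variables in SAP section 2; the protocol lists it but the SAP does not. For knees without a linked primary, use that number plus 1 as the grade in the all-revision series only. The field is listed without a major/minor split, so it cannot give a major-revision grade.
4. Where the field is missing, and for major-revision grades where the earlier history is not known, show the revision in a *grade unknown* row.
5. Show the PRIM-linked cohort as a second series with known grades, keep it for WP-A2, and do not read its early years as a trend.
6. Compare annual all-grade totals with the register's totals and explain differences due to the LPR merge and the spacer rules. An exact match should not be required.
7. State that knees last revised before 1998 remain outside prevalence.

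The records are already held. The cost is new SAP wording, some linkage and status tracking for knees outside PRIM, a second run, and a visible *grade unknown* row, mainly in the early years.

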### Further statistical details

**Power considerations:** A sample size calculation has not been performed, as our sample will be determined solely by the actual number of eligible patients available from the registries.

**Framework:** This is an observational study aimed at reporting the prevalence and incidence of multiple revised knee arthroplasty patients in Denmark. No formal statistical testing will be performed.

**Statistical interim analyses and stopping guidance:** Not applicable.

**Timing of final analysis:** Access to all data has been acquired. The final analysis will be performed after the completion and acceptance of the SAP by all participants.

**Timing of outcome assessment:** (see next section).

**Confidence intervals and P values:** Not applicable.

**Multiplicity:** No formal statistical testing will be performed.

**Statistical software:** R, version 4.3.0 (or newer).

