Year	1 st revision	2 nd revision	....	n grade revision	Maximal grade of revision performed*
1998					
1999					
2000					
2001					
2002					
2003					
2004					
2005					
2006					
2007					
2008					
2009					
2010					
2011					
2012					
2013					
2014					
2015					
2016					
2017					
2018					
2019					
2020					
2021					

Only grades of revisions with occurrences >10 for all years are shown

\*The maximal grade of revision performed is defined as the single greatest grade of revision performed that year

[figure not shown]
**Figure 2.** The standardized prevalence and incidence rates of n-grade revisions from 1998 to 2021.

*Anticipated plot design, illustrating with imaginary data, A-D*

Panel A and B illustrates standardized prevalence and incidence of major n-grade revisions. Panel C and D illustrate standardized prevalence and incidence of all n-grade revisions (including both major and minor revisions). Only grades of revisions with occurrences >10 are shown; for prevalence, >n-grade revisions are reported as well.

**Figure 3.** The standardized prevalence of patients with their total sum of revisions.

Panel A illustrates standardized prevalence of patients with major n-grade revisions. Panel B illustrates standardized prevalence rates of patients with all n-grade revisions (including major and minor revisions). The total sum of revisions is the summation of all revision procedures performed on a patient. E.g., a patient with 3 revisions performed on one knee and 4 revisions performed on the other knee, is categorized as a 7-grade revision patient. Only grades of revisions with occurrences >10 are shown as well as >n-grade grade revisions.

[figure not shown]

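### The SAP rules out confidence intervals although it hypothesises an increase and plots annual incidence for rare revision grades and strata, where chance variation can be large

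*SAP*

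**What the plan says.** - **Hypothesis** (SAP section 1): "The number and burden of knee arthroplasty revision procedures and patients in Denmark has increased dramatically in the last 23 years".
- **Primary outcome** (SAP section 1, PICOTS): "Annual standardized prevalence and incidence of n-grade revisions following knee arthroplasty between 1998 and 2021 in Denmark". SAP section 3 defines each rate as a count divided by the Danish population on 1 January, times 100,000, for every grade and year. Neither formula has a measure of uncertainty.
- **Inference** (SAP section 1, Further statistical details): "No formal statistical testing will be performed". The entry headed "Confidence intervals and P values" reads *Not applicable*, with no reason. Item 17 of the reporting checklist (SAP section 7, Table A), on confidence intervals, points back to this section.
- **Sample size** (same section): none is calculated, because the registers fix the number of patients.
- **Displays** (SAP section 5 and supplementary material): Tables 2 and 3 give annual counts by grade. Figure 2 plots annual incidence and prevalence by grade. Supplementary Figures 1 to 10 repeat this by sex or by age group, and Supplementary Tables 1 to 4 cross sex with age for 2021.
- **Display rule**: the notes to Table 2 and Figure 2, and those in the supplement, say "Only grades of revisions with occurrences >10 are shown". Table 3 says "Only grades of revisions with occurrences >10 for all years are shown". The unit of the count (each year, or the whole period) is not stated.

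The protocol's statistics section for WP-A1 names no interval or trend estimate over calendar time either.

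**The concern.** Complete national coverage removes sampling error. It does not remove random year-to-year variation in a rare event: the same underlying rate can produce 11 operations in one year and 18 in the next. The study's stated interest is in knees with three or more revisions, which is where counts become small. Splitting by sex or age makes them smaller again.

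With bare points on a graph, a reader cannot see which movements in a rare grade exceed chance. Because the SAP states in advance that it expects a rise, chance movement in that direction is likely to be read as confirmation.

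**Working it through.** The plan states no interval, significance level or sample size, so it has no figure of its own to reproduce. The check asks how wide the omitted intervals would be.

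**Inputs**
- Smallest count above 10: 11 (display rule, SAP section 5), if the rule applies per year.
- All revisions in one year: 1048 in 2020 (protocol, Background, Size of the problem).
- Calendar years: 2021 − 1998 + 1 = 24.
- Counts by grade are not in the documents, so 11, 20, 22 and 24 are illustrations anchored at the display threshold.

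**Interval for one annual count.** The exact 95% Poisson limits for a count k are χ²(0.025; 2k)/2 and χ²(0.975; 2k+2)/2.

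| Count | Lower | Upper | Relative to the count |
|---|---|---|---|
| 11 | 5.49 | 19.68 | 0.50 to 1.79 |
| 20 | 12.22 | 30.89 | 0.61 to 1.54 |
| 50 | 37.11 | 65.92 | 0.74 to 1.32 |
| 100 | 81.36 | 121.63 | 0.81 to 1.22 |
| 1048 | 985.5 | 1113.4 | 0.94 to 1.06 |

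For 11: χ²(0.025; 22)/2 = 5.49 and χ²(0.975; 24)/2 = 19.68. Dividing count and limits by the same population leaves the relative width unchanged, so no population figure is needed.

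**Ratio of two annual counts.** Assume equal populations in the two years. Given the total a + b, the later count b is binomial. With Clopper-Pearson limits p for its share, the ratio limits are p/(1 − p).

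- 11 then 20: ratio 1.82, interval 0.83 to 4.20.
- 11 then 22: share limits 0.482 and 0.820, so 0.482/0.518 = 0.93 and 0.820/0.180 = 4.57 (from unrounded limits). Ratio 2.00, interval 0.93 to 4.57.
- 11 then 24: ratio 2.18, interval 1.03 to 4.93.

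At this count a plotted doubling between two years is compatible with no change.

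**If the rule is a total over the period.** Eleven events over 24 years average 11/24 = 0.46 a year. Single-year points would often be 0 or 1, with exact intervals 0 to 3.7 and 0.03 to 5.6.

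**A whole series instead of two years.** Suppose expected counts rise log-linearly from 11 to 22 over the 24 years, with constant population. A Poisson regression on year then has a standard error of about 0.172 for the log ratio of last to first year. The interval is exp(0.693 ± 1.96 × 0.172), about 1.4 to 2.8. A smooth trend over the full series can therefore be distinguished from chance where a pair of years cannot.

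**What a trend would contain.** The SAP's population is limited to primaries from 1998 (PICOTS), and prevalence counts only revisions from 1998 (section 3). A knee must pass through grades 1 and 2 inside this window before it can count as grade 3. Higher grades therefore start near zero and rise by construction, whatever the underlying rate does.

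**The case against.** The strongest case against is that this is a descriptive study of a complete national count. The hypothesis speaks of realised numbers in one country over a fixed period, and for all revisions together random variation is about ±6%. Sparse grades are suppressed, and Tables 2 and 3 publish raw annual counts, from which a reader could compute intervals for national incidence. On this view, intervals on a full count are largely a matter of preference.

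Much of this stands, and it limits the point. Two stronger readings are tempting, and the documents do not support them:

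- *That nothing planned bears on the hypothesis.* The annual counts and rates are the quantities it names. What is absent is a criterion for "has increased dramatically in the last 23 years" and a measure of uncertainty.
- *That a rise can never be told from noise.* The comparison of 11 with 22 sets two isolated years at the display threshold. Readers get up to 24 points, and the series calculation shows that a sustained doubling would be visible.

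Three things do not fall to the objection. The display rule admits counts of 11, and perhaps fewer. The published counts do not cover the annual sex and age strata in Supplementary Figures 1 to 10. Intervals are not tests, so adding them is consistent with the decision to do no formal testing. The SAP itself does not offer complete coverage as its reason.

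**Conclusion.** The concern holds in a limited form. Excluding intervals is a weakness for annual incidence in the higher grades and in the sex and age strata; it is not one for overall revision counts. At 11 events the 95% interval runs from about half to 1.8 times the plotted value, and a doubling to 22 in another year has an interval of 0.93 to 4.57.

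This rests on three assumptions: Poisson variation, equal populations in the two years compared, and a display rule applied per year. A reader might take 11 as the plan's stated minimum for every plotted rate. The SAP does not say so, because the unit of the rule is open. Read as a period total, annual counts could be lower. Actual counts by grade are unknown, so how many displayed points are affected cannot be determined from the documents.

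A reader might also infer that every plotted rate needs a Poisson interval and that each grade needs a 1998 to 2021 trend. Neither follows. Prevalence carries the same living knees from year to year, so year-by-year Poisson intervals are strongly dependent and would mislead about its trend. An unqualified annual percentage change for higher grades would put a precise interval around a partly artefactual rise. The point is an inexpensive improvement to a stated rule. It does not invalidate the planned description.

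**What to change.** 1. In SAP section 1, replace *Not applicable* with exact Poisson 95% intervals for annual incidence by grade, shown in Figure 2 and in the sex and age strata. No P values are needed.
2. Do not use year-by-year Poisson intervals to judge prevalence trends, and say why: the same knees recur each year.
3. Choose one of two courses for the hypothesis. Either add a trend summary for incidence with its interval (for example a rate ratio per year from Poisson or negative binomial regression with log population as offset), qualified for the 1998 start or restricted to later years; or word the hypothesis as descriptive.
4. State whether the threshold of more than 10 applies per year, in every year or in total, and use one wording throughout.

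The cost is a few lines of R, busier figures, and one sentence explaining that the intervals describe random variation in a fully counted population. No new data are needed. A restricted trend also requires a reasoned choice of start year, made before the analysis.
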